Study Title: A Pilot Study Investigating the nCAP Signal Relief Patch in Subjects Undergoing Primary Hip or Knee Replacement Surgery – A Pilot Trial

Principal Investigator: [name], PhD, MBA

IRB: STUDY22010018 NCT: 05252858

Statistical Analysis Plan Approval Date: 02/01/2022

Power calculation is for an anticipated 60 subjects who underwent TKA. Data is to be analyzed using intend-to-treat analysis plan. Data collection in this study includes the following measurements:

- Total opioid consumption (OME mg),
- Pain at rest and during movement rated on a standard Numerical Rating Scale (NRS, 0 = no pain and 10 = the worst pain imaginable),
- Area under the curve (AUC) for pain scores collected on POD 1, 2, 3, 7, 14, and 30,
- Time to discharge from the recovery room,
- Time to discharge from the hospital, and
- Overall subject satisfaction at the time of hospital discharge

The number of subjects requesting a prescription refill during the first 30-days post-operative will be calculated using the Pennsylvania Data Management Program.

Student's t-test, non-parametric Kruskal-Wallis test, or Pearson's chi-square test were used to determine differences in the distribution of continuous outcomes, and the chi-square test or exact test was used for differences in proportions for categorical outcomes between the treatment and placebo arms. Data will be presented as mean \pm standard deviation (SD) with a standard alpha set at 0.05.

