- 1. The primary endpoint will be to prospectively investigate the efficacy of the nCAP Signal Relief Patch in reducing perioperative opioid requirement (up to 72 hours post-op) in opioid-naïve patients undergoing primary unilateral total hip or knee replacement surgery. Opioid requirement will be estimated following the placement of the patch.
- 2. The secondary endpoint will include the effects of nCAP Signal Relief Patch after the placement on postoperative pain, functional recovery, time to discharge from the hospital, and opioid related complications, such as, PONV, itching, sleep disorders, respiratory depression, and urinary retention.

Study Design

The proposed pilot study will be conducted as a single-center prospective, randomized, open label trial at the University of Pittsburgh Medical Center (UPMC) Shadyside Hospital.

Institutional review board approval will be obtained before eligible patients are recruited and consented. The trial will be registered at www.clinicaltrial.gov before beginning recruitment.

The efficacy of this device will be established by comparing postoperative opioid requirement to maintain pain scores \leq 4 using a Numerical Rating Scale (NRS). Accordingly, pain will be treated according to the following protocol: pain scores \leq 4, non-opioid analysics, pain scores between 4 and 6 oxycodone 5 mg q 4 hrs and \geq 7, oxycodone 10 mg, Hydromorphone IV 0.2-0.5 mg q 3 hr. Data collected following the placement in the treatment group (Standard of Care ERAS protocol + nCAP Signal Relief Patch) will be compared to the data obtained in the control group (Standard of Care ERAS protocol).

Recruitment

Potential subjects may be given a recruitment flyer (attached) in the office of surgeons Drs.

[name], [name], or [name]. The potential subjects who receive a flyer will then have the option of contacting the study team to discuss the study further, or, if they express interest in participating in the surgeon's office, their name will be given to the study team from the surgeon's office staff.

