Potential subjects may also be identified by the study team who has normal access to the Operating Room Schedule and electronic medical records. If a subject is deemed eligible via inclusion/exclusion criteria, a study team member will approach them the morning of their scheduled surgery and discuss the study with them at length and answer any questions they may have. If a potential subject is willing to sign consent, then a physician investigator will be available to review the consent, risks and benefits of participation, and obtain informed consent.

If our research team is contacted prior to the day of surgery, or if we reach out based upon the list of interested potential subjects, study team will discuss the study at length over the phone and answer any questions the potential subjects may have. Subjects interested in participating will be emailed the currently approved informed consent form to review. They will be given the option to sign consent electronically for convenience via REDCap or they can sign consent form on the day of surgery in the pre-operative holding area.

The subject will be approached as soon as they arrive to the hospital (at least 2-3 hours before their surgery) and will be given adequate time to consider the consent and ask questions. The patient will be urged to take as long as necessary to decide whether or not to participate. If the

subject feels they do not have enough time to make a decision, they will not be enrolled in the trial.

All questions will be addressed and it will be made clear that the patient may withdraw from the study at any time. Investigator physician will sign the informed consent with the patient prior to beginning of any study procedures.

Randomization Process

Participating patients will be randomized by computer-generated random numbers to either the control group (standard of care ERAS protocol) or intervention group (nCAP Signal Relief Patch group+ ERAS protocol).

Inclusion Criteria:

- Over 18 years of age
- Scheduled for elective primary unilateral hip or knee replacement surgery

Exclusion Criteria:

- Active clinical depression, anxiety, or catastrophizing
- Raw score equal to or greater than 19 on the PROMIS Anxiety 8a Adult v1.0
- Active alcoholism or drug abuse
- Severe chronic pain condition that requires daily preoperative opioid dependence
- Total surgery revision, bilateral hip replacement, multiple surgeries

Treatment Groups

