Each subject will undergo surgery and anesthesia using the approved ERAS protocol.

Control Arm (n=30): Control group will receive approved ERAS multimodal anesthesia protocol (standard of care).

Interventional Arm (n=30): Intervention group will receive approved ERAS multimodal anesthesia protocol plus an nCAP Signal Relief Patch.

Data Collection and Outcome Measures

After signing an informed consent, subjects will complete the PROMIS Emotional Distress – Anxiety – Short Form 8a before completing any other questionnaires. Subjects who have a raw score <19 will be enrolled in the study. Any subject who scores \ge 19 will be considered a screen failure and excluded from the study.

Once the subject is enrolled, they will be asked to complete the Pain Catastrophizing Scale (PCS), the PROMIS® Emotional Distress-Depression - Short Form 8a, and the PROMIS® Item Bank v1.0 – Sleep- Disturbance – Short Form 8a prior to surgery. The subject will also conduct a baseline functionality test to assess mobility and strength in their leg. The functional recovery will be assessed by determining the patient ability to walk 100 feet, go up 5 steps and raise their leg on the day of surgery. Scores can be 0 (no ability to raise the leg), 1 (some ability to raise the leg), and 2 (complete ability to raise the leg).

Once these assessments are completed, subjects will be equally randomized to the intervention group (nCAP signal relief Patch + standard of care) or control group (standard of care). Both the control group and intervention group will receive approved ERAS multimodal standard of care. Only the interventional group will receive an nCAP Signal Relief Patch.

Randomization will occur by assigning the participant a subject ID number, and this ID number will correspond to a treatment allocation based on a pre-designed randomization schema.

Subjects will undergo surgery using the approved ERAS anesthetic and post-operative pain management protocols.

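### The SAP's sample-size sentence names 60 knee-replacement subjects, but the trial randomises 30 + 30 hip-or-knee patients, and the listed tests take no account of joint

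*SAP*

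**What the plan says.** **Sizing.** The SAP's only sample-size statement is "Power calculation is for an anticipated 60 subjects who underwent TKA". It gives no target difference, SD, power or sidedness. An alpha of 0.05 appears at the end of the SAP.

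**Population.** The SAP title refers to "Subjects Undergoing Primary Hip or Knee Replacement Surgery". The Protocol's primary aim (Specific Aims) concerns "patients undergoing primary unilateral total hip or knee replacement surgery", and its Inclusion Criteria read "Scheduled for elective primary unilateral hip or knee replacement surgery".

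**Allocation.** The Protocol's Treatment Groups section gives 30 per arm and sets no number for either joint. Data Collection and Outcome Measures adds: "Once these assessments are completed, subjects will be equally randomized to the intervention group". On method, the Randomization Process section mentions only random numbers produced by computer. Data Collection and Outcome Measures mentions an allocation schema drawn up in advance and does not describe it.

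**Analysis.** The SAP lists Student's t, Kruskal-Wallis, chi-square and exact tests between the arms. No covariate, stratum or subgroup for joint appears.

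**The concern.** TKA is knee replacement. A calculation for 60 knee patients does not describe a trial that pools hips and knees in whatever mix presents. Since no inputs are given, a reader cannot tell which patients or what effect the 60 was meant to address. That matters even in a pilot, because the Protocol (Pre-and-Post Metric Evaluation) says the data will support a proposal for a full-scale trial.

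The second part follows from the first. If opioid use differs between hip and knee patients, that difference becomes extra noise in an unadjusted comparison. Joint is known before randomisation, so the noise could be removed at little cost.

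**Working it through.** **1. The plan's own figure.** 30 + 30 = 60, so the count agrees with the SAP. The 60 cannot be derived from an effect, because no difference, SD or power is given. The conflict is in the population.

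**2. Could the documents reconcile it?** The SAP is dated 02/01/2022 and the Protocol approval 08/10/2022, so a later widening of eligibility might be suspected. But the SAP conflicts with its own title, so timing does not explain it.

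**3. What 30 per arm gives.** Unit: the within-joint SD of opioid use. Assumed: two-sided 0.05, complete and normal outcomes.
- SE of the difference = √(2/30) = 0.258.
- Single-joint population, or list balanced by joint: 95% CI half-width = 2.002 × 0.258 = 0.517. By the noncentral t, 80% power is reached at 0.736 SD.
- Joint in a linear model, unstratified list: chance imbalance of joint between arms multiplies the variance by 1.018 on average. Half-width = 2.002 × 0.258 × √1.018 = 0.522, and 80% power is reached at 0.742 SD. Power at 0.736 SD is 79.3%.

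Both cases round to 0.52 and 0.74.

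**4. Leaving joint out, unstratified list.** Let p be the share of hips and D the hip-knee gap in within-joint SDs. The variance is multiplied by 1 + p(1 − p)D². Neither p nor D is in the documents, so the values below are assumptions. Power is at a difference of 0.736 SD, and the last column subtracts the rounded figures.

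| D | p | Variance factor | Unadjusted power | Adjusted power | Net change from adjusting (points) |
|---|---|---|---|---|---|
| 0 | any | 1.000 | 80.0% | 79.3% | −0.7 |
| 0.25 | 20% | 1.010 | 79.6% | 79.3% | −0.3 |
| 0.25 | 50% | 1.016 | 79.4% | 79.3% | −0.1 |
| 0.5 | 20% | 1.040 | 78.4% | 79.3% | +0.9 |
| 0.5 | 50% | 1.063 | 77.6% | 79.3% | +1.7 |
| 1.0 | 20% | 1.160 | 73.9% | 79.3% | +5.4 |
| 1.0 | 50% | 1.250 | 70.7% | 79.3% | +8.6 |

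Adjustment breaks even where p(1 − p)D² = 0.018: D = 0.34 for 20% hips and D = 0.27 for 50% hips.

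**5. If the list is in fact stratified by joint.** Simulation (40,000 trials per cell, gaps 0.5 and 1.0 SD, 20% and 50% hips) gives the unadjusted t-test 79% down to 72% power and a type I error of 4.7% down to 2.8%. The adjusted analysis stays at about 80% power and 5% error.

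**The case against.** The strongest reply is that the documented error is one abbreviation. With the SAP title and two Protocol sections all saying hip or knee, TKA may be a slip. An unadjusted t-test or rank test is also valid in a randomised pilot, and the gain from adjustment depends on a hip-knee gap that the documents do not give. Much of this stands. The gain is small at a gap of 0.5 SD and slightly negative at 0.25 SD, so adjustment is a cheap improvement and not the repair of an invalid test. But a slip still has to be corrected, and only the sponsor can say which text is wrong. Correcting the word would also leave the 60 without inputs.

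A reader might go further in several ways that the documents do not support:
- **That 60 is too few.** With no target effect there is nothing to fall short of.
- **That pooling joints biases the comparison or inflates type I error.** Randomisation protects against both. In simulation the unadjusted error was 4.7% to 5.1% on an unstratified list, and below 5% on a stratified one.
- **That adjustment restores the whole fall from 80% to 71%.** On an unstratified list the adjusted analysis itself has 79.3%, so the net changes in the table are the fair comparison.
- **That allocation is unstratified.** It is unstated. Computer-generated numbers and an undescribed schema fit either case.
- **That the 70 enrolled in Pre-and-Post Metric Evaluation shows a dropout allowance.** No document states a loss rate.

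**Conclusion.** The inconsistency is certain on the text: the sizing sentence names knee replacement, while the SAP title and the Protocol's aims and inclusion criteria say hip or knee. It is also certain that the 60 has no stated inputs and that the listed tests omit joint.

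The practical cost of omitting joint is less certain. On an unstratified list with 20% to 50% hips, adjusting gains about 1-2 points of power at a gap of 0.5 SD and about 5-9 at 1.0 SD, and loses under half a point at 0.25 SD. These figures rest on assumed joint shares and gaps, complete normal outcomes and a two-sided 0.05 test. The point should be fixed, but it does not threaten the validity of the trial.

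**What to change.** **1. Confirm the population.** If it is hip or knee, replace the TKA sentence with:

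> 60 patients having primary unilateral hip or knee replacement are randomised, 30 per arm. This number was not derived from a target effect. With complete outcomes and joint as a factor, it gives a 95% CI half-width of about 0.52 within-joint SD for the difference in opioid use to 72 hours (equivalently, 80% power at two-sided 0.05 for about 0.74 SD).

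The 0.74 is worked back from the sample size and must not be presented as a planned effect. If a real prospective calculation exists, state its inputs for the hip-or-knee population instead. If only knees were meant, the SAP title and the Protocol's aims, inclusion criteria and treatment groups must be reconciled with that, and step 2 falls away.

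**2. Prespecify joint (hip/knee) as a factor in the primary opioid analysis.** If a rank test is used, stratify it by joint. The 0.74 does not carry over exactly: in simulation with normal outcomes, the joint-stratified rank test had about 76-77% power near that difference. State also whether the randomisation list is stratified by joint.

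**Cost.** SAP wording and one baseline factor already known before surgery. It uses one degree of freedom and loses at most about 0.7 point of power if joint has no effect. No extra patients or data are needed under the hip-or-knee reading.

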After surgery, the subjects randomized to the intervention group will have the nCAP Signal Relief patch applied to their surgical dressing by a trained researcher in the immediate Post Anesthesia Care Unit (PACU). Subjects will be made aware at the time of consent and throughout the trial that they can drop out of the study at any time if they do not like wearing the nCAP Signal Relief Patch. The control group will not receive a patch but will receive the standard of care ERAS protocol. Subjects in the intervention group will be instructed to keep the nCAP Signal Relief Patch on their surgical dressing to avoid the risk for skin irritation.

Pain using a Numerical Rating Scale (NRS) at rest and with movement as well as opioid requirement will be assessed in the PACU and daily until discharge.

Subjects assigned to the intervention group should keep the nCAP Signal Relief Patch in place for 72 hours on their surgical dressing and they will be instructed to remove it at home.

Once the subject is discharged, they will be asked to complete a pain and opioid diary to record pain-related outcomes. They will be contacted via email (REDCAP survey) on post-operative day 1,2,3, 7, 14, and 30 to record postoperative opioid consumption, non-opioid consumption, NRS pain at rest and with movement, pain catastrophizing (via Pain Catastrophizing Scale) sleep quality (via PROMIS Sleep Disturbance Short Form 8a) and to assess functional recovery. Functional recovery will be assessed by determining the patient ability to walk 100 feet, go up 5 steps and raise their leg on postoperative days 1, 2, 3, 7, 14, and 30 as well as the pain associated with it. Patient satisfaction with pain management after surgery will be assessed at the 30 day follow up (0- least satisfied to 10-most satisfied). Subjects who are contacted via REDCap to complete follow-up questionnaires and do not complete them on the day they are assigned will be contacted via telephone for a reminder. They will be considered lost to follow up after 3 phone attempts.

Information will be collected from the medical record, including: patient demographics, medical history, medication summary while in the hospital, as well as progress notes from the entire encounter to determine the existence of adverse events.

Pre-and-Post Metric Evaluation

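### The primary opioid count starts at patch placement, which controls never have; the SAP omits the 72-hour endpoint, assigns it no single test, lists chi-square for continuous data and calls the control 'placebo'

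*SAP*

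**What the plan says.** - **Tests (SAP, closing paragraph).** "Student's t-test, non-parametric Kruskal-Wallis test, or Pearson's chi-square test were used to determine differences in the distribution of continuous outcomes". The next clause assigns chi-square or an exact test to categorical outcomes. There is no rule for choosing among the tests for continuous outcomes. Alpha is 0.05, with no statement of one or two sides. The protocol names no test.
- **Opioid outcome (SAP, list of measurements).** "Total opioid consumption (OME mg" is the first of six bullets. None is labelled primary, and this one has no time window.
- **Primary endpoint (Protocol, Specific Aims).** The aim is efficacy "in reducing perioperative opioid requirement (up to 72 hours post-op" after hip or knee replacement. The same item adds: "Opioid requirement will be estimated following the placement of the patch".
- **Patch placement (Protocol, Data Collection and Outcome Measures).** In the intervention arm the patch is "applied to their surgical dressing by a trained researcher in the immediate Post Anesthesia Care Unit (PACU". Controls get no patch. Opioid use is assessed in the PACU and daily until discharge, and patients are then contacted "on post-operative day 1,2,3, 7, 14, and 30 to record postoperative opioid consumption" among other outcomes.
- **Control arm.** The protocol's Study Design describes a "single-center prospective, randomized, open label trial" with ERAS care alone as the comparator. The SAP makes its comparison "between the treatment and placebo arms".

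**The concern.** The primary outcome needs a quantity, a start, an end and a test. Across the two documents the quantity (OME in mg) and the end (72 hours) can be found. The start is tied to an event in one arm only, and the test is left open.

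The start matters most, because it can treat the arms differently. Suppose an analyst counts from placement in the patch arm and from PACU arrival in controls, for want of anything else. Doses given between arrival and placement then count for controls only, and the comparison favours the patch before the patch has done anything.

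The open test matters less. If the choice were made after seeing the results, the 5% level would not be guaranteed. Chi-square has no meaning for a continuous amount unless a cut-point is set, and none is given. The word 'placebo' affects no calculation, but taken into a report it would suggest that patient expectation was controlled when it was not.

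**Working it through.** **No figure to reproduce.** The SAP's 60 subjects cannot be re-derived, because it gives no effect size, SD or power. The point does not depend on that number.

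**1. The window, arm by arm**

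| | Patch arm | Control arm |
|---|---|---|
| End (Protocol, Specific Aims) | 72 h post-op | 72 h post-op |
| Start (Protocol, Specific Aims) | patch placement, in the PACU | no such event |
| Window in the SAP | none given | none given |

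The end is common to both arms and the start is not. Let *m* be the mean OME given between PACU arrival and patch placement. Randomisation makes *m* the same in expectation in both arms. If controls are counted from arrival and patch patients from placement, then with no patch effect at all:

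expected difference (control − patch) = (*m* + later use) − (later use) = *m*

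The bias is *m* mg in favour of the patch. The documents give neither the time from arrival to placement nor the opioid used in it, so *m* has a known direction but no known size. With one start for both arms, *m* cancels.

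**2. Type I error if the test is left open**

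Inputs: 30 per arm (Protocol, Treatment Groups) and alpha 0.05 (SAP). Assumed: two-sided testing, and OME either lognormal with log-SD 0.6, 0.8 or 1.0, or normal. The documents give no SD or shape.

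- t-test: t = (mean₁ − mean₂) / [s_p √(1/30 + 1/30)], on 58 df.
- Kruskal-Wallis with two arms is the Wilcoxon rank-sum test: z = (R − n(2n+1)/2) / √(n²(2n+1)/12). With n = 30 the centre is 30 × 61/2 = 915 and the SD is √(900 × 61/12) = √4575 = 67.6.
- Written rule: t-test if Shapiro-Wilk gives p > 0.05 in both arms, otherwise the rank test.
- Free choice, worst case: reject if the smaller of the t and rank p-values is below 0.05.

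Simulated rejection rates with no true difference (%):

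| Assumed data | Fixed t | Fixed rank | Written rule | Smaller p |
|---|---|---|---|---|
| Lognormal, log-SD 0.6 | 4.79 | 4.96 | 5.20 | 6.75 |
| Lognormal, log-SD 0.8 | 4.48 | 4.96 | 4.74 | 6.78 |
| Lognormal, log-SD 1.0 | 4.12 | 4.96 | 5.17 | 6.87 |
| Normal | 4.93 | 4.96 | 5.05 | 5.88 |

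The t and smaller-p columns use 100,000 replicates (SE about 0.07 points at 5%). The written rule uses 15,000 (SE 0.18 points). The rank figure is exact by enumeration, assuming no ties. A repeat of the lognormal smaller-p column with 40,000 replicates gave 6.7, 6.8 and 6.8%, hence the range 6.7 to 6.9%.

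So any one choice fixed in advance stays at or near 5%. Picking the better result adds just under 2 points under the assumed skew (6.87 − 5 = 1.87) and about 0.9 with normal data (5.88 − 5 = 0.88).

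**3. Chi-square and 'placebo'**

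Both are settled by reading. The SAP sentence names chi-square for continuous outcomes and then again for categorical ones, where it belongs. The protocol describes an open-label comparison with a no-patch control and, in Pre-and-Post Metric Evaluation, leaves a placebo-controlled trial to a later proposal.

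**The case against.** **The window is in the protocol.** This stands. A reader might infer from the SAP's unqualified total, and from collection to day 30, that the primary outcome could equally be 72-hour or 30-day use. The documents do not support that: Specific Aims limits the endpoint to 72 hours, and nothing calls the later data primary. What remains is that the SAP does not carry the endpoint over.

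**The arms do share an anchor.** The 72 hours run post-op for everyone, opioid use is assessed in the PACU without restriction to one arm, and the patch goes on early in the PACU stay. This narrows the gap to the interval before placement. It does not close it, because Specific Aims still counts from placement and gives controls no equivalent.

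**Chi-square is a drafting slip.** Probably so. A reader might infer that OME will be dichotomised, but no cut-point or split is mentioned, so there is no such analysis whose error rate could be assessed. The wording is still wrong and should go.

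**The open test is missing detail in a pilot, with small consequences.** Largely fair. A reader might infer that the test will be picked after the results are known. Nothing shows this, and a written normality rule would keep the level close to 5%. The SAP does, however, set a 5% alpha for a trial whose primary aim is efficacy, and the protocol does not supply a test.

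**Nobody would be misled by 'placebo'.** Not with the protocol in hand, since its title says open label. It remains a contradiction that takes one word to correct.

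**Conclusion.** The point holds in a limited form.

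- **Start of the count:** a real inconsistency in the protocol. It can bias the comparison towards the patch by the mean opioid use between PACU arrival and placement if the arms are counted differently. The size is unknown from the documents and is limited to that interval.
- **SAP against protocol:** the 72-hour primary endpoint is not carried over, and no single test is attached to it. The worst-case type I error from choosing between the t and rank tests is about 6.7 to 6.9%. This rests on 30 per arm, two-sided 5% and assumed lognormal OME; under assumed normal data it is 5.9%. It describes what an open choice allows and is not evidence that one was made.
- **Chi-square for continuous outcomes and 'placebo':** both wrong as written. The first is probably a slip; the second is minor and does not affect alpha.

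These should be corrected because they concern the primary analysis and cost little. They do not show that the trial lacks a primary window or that its 5% level has been lost.

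**What to change.** 1. **Both documents:** define the primary outcome as OME to 72 hours from one start that exists in both arms. PACU arrival is one example. Because arrival precedes placement, the Specific Aims sentence that starts the count at placement must be amended as well; editing the SAP alone would leave the two in conflict.
2. **SAP:** label this outcome primary and assign it one two-sided test in advance. A rank test, a t-test or a written selection rule would each hold the level at or close to 5%.
3. **SAP:** delete chi-square from the tests for continuous outcomes.
4. **SAP:** replace 'placebo' with 'control (ERAS only)', and word the conclusion as the effect of adding an open-label patch to ERAS care.

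**Cost:** a small change of wording in both documents. With PACU arrival as the start, opioids given before placement count in both arms although the patch cannot affect them. That may slightly dilute the effect: the expected difference in mg is unchanged, but the relative reduction shrinks and some variability is added.
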